## 1. VERSION HISTORY

This SAP for study C1071004, Sub-Study B is based on the protocol amendment v6.0 (dated 02 December 2021). Sub-study B was first added under the Master Protocol Amendment 4 dated 09 Aug 2021, which was intended for FDA’s review and endorsement. The sub-study B protocol amendment v5.0 was done as of 08 Nov 2021 per FDA’s comments, amendment v6.0 was done as of 02 Dec 2021. It’s then decided the sub-study B SAP v1.0 will be generated to align with amendment 6. No participants were enrolled prior to protocol amendment v6.0.

**Table 1. Summary of Changes**

Version/ Date	Associated Protocol Amendment	Rationale	Specific Changes
1 28 Jan 2022	Amendment 6.0		

## 2. INTRODUCTION

This SAP provides the detailed methodology for summary and statistical analyses for sub-study B of C1071004 umbrella study. C1071004 sub-study B is a prospective, open-label, multi-center, Phase 1b study to evaluate safety, efficacy, PK, and pharmacodynamics of elranatamab in combination with lenalidomide and dexamethasone in participants with Relapsed/refractory multiple myeloma (RRMM):

- **Dose escalation part** is to evaluate the tolerability, safety and select a recommended dose and regimen for elranatamab in combination with lenalidomide and dexamethasone (combination RP2D).
- **Dose expansion part** is to further evaluate the overall safety of the combination at RP2D.

The general methodology for summary and statistical analyses that apply to all sub-studies in the umbrella protocol are described in the Master SAP. This SAP provides statistical methodology and analyses that are specific to sub-study B.

## 2.1. Study Objectives, Endpoints, and Estimands

### Dose Escalation Part

Type	Objectives	Endpoints	Estimands
Primary			
Safety	
 
To assess safety and tolerability of elranatamab in combination with lenalidomide and dexamethasone in participants with RRMM in order to select a RP2D(s) for the combination
 
	
 
DLTs during DLT observation period.
 
	
 
The primary estimand is DLT rate estimate based on data from DLT-evaluable participants during the DLT observation period, which is 42 days from C0D1 through C1D28.
 

Secondary			
Safety	
 
To evaluate the overall safety profile of elranatamab in combination with lenalidomide and dexamethasone
 
	
 
AEs as characterized by type, frequency, severity as graded by NCI CTCAE version 5.0, timing, seriousness, and relationship to elranatamab in combination with lenalidomide and dexamethasone. The severity of CRS and ICANS will be assessed according to ASTCT criteria (Lee et al, 2019);
 
Laboratory abnormalities as characterized by type, frequency, severity (as graded by NCI CTCAE version 5.0), and timing.
 
	
 
N/A
 

Efficacy	
 
To evaluate anti-myeloma activity of elranatamab in combination with lenalidomide and dexamethasone
 
	
 
ORR and CRR, per IMWG response criteria as determined by investigator;
 
Time to event endpoints: TTR, DOR, DOCR, PFS per IMWG response criteria as determined by investigator, and OS;
 
MRD (assessed by central lab) negativity rate per IMWG sequencing criteria.
 
	
 
N/A
 

090177e1993a4a6d\Approved\Approved On: 31-Jan-2022 16:54 (GMT)

PK	
 
To evaluate the PK of elranatamab given alone and in combination with lenalidomide and dexamethasone
 
	
 
Free and total PK parameters of elranatamab in serum: <math>C_{max}</math>, <math>T_{max}</math>, <math>AUC_{last}</math> after elranatamab administration alone as a priming dose.
 
	
 
N/A
 

	
 
To evaluate the PK of lenalidomide when administered with elranatamab
 
	
 
Pre- and post-dose concentrations (free and total) of elranatamab in combination with lenalidomide and dexamethasone;
 
Trough plasma concentrations of lenalidomide at selected cycles.
 
	
 
N/A
 

Immunogenicity	
 
To evaluate immunogenicity of elranatamab in combination with lenalidomide
 
	
 
Incidence and titers of ADA and NAb against elranatamab.
 
	
 
N/A
 

Tertiary/Exploratory			
Biomarker	
 
To explore correlations between elranatamab exposure and efficacy, safety, and biomarker endpoints, if data allow
 
	
 
Selected PK, efficacy, safety, and biomarker endpoints.
 
	
 
N/A
 

	
 
To understand the relationship between elranatamab in combination with dexamethasone and lenalidomide and the biology of the participant's MM
 
	
 
Measurements of biomarkers (DNA, RNA, protein, or defined cell types) resulting from analyses of peripheral blood and/or BM biospecimens.
 
	
 
N/A
 

PRO	
 
To assess the impact of elranatamab on patient-reported symptoms and functioning
 
	
 
EORTC QLQ-CIPN20.
 
	
 
N/A
 

090177e1993a4a6d\Approved\Approved On: 31-Jan-2022 16:54 (GMT)

**Dose Expansion Part**

Type	Objectives	Endpoints	Estimands
Primary			
Safety	
 
To evaluate the overall safety profile of elranatamab in combination with lenalidomide and dexamethasone
 
	
 
AEs as characterized by type, frequency, severity as graded by NCI CTCAE version 5.0, timing, seriousness, and relationship to elranatamab in combination with lenalidomide and dexamethasone. The severity of CRS and ICANS will be assessed according to ASTCT criteria (Lee et al, 2019).
 
Laboratory abnormalities as characterized by type, frequency, severity (as graded by NCI CTCAE version 5.0), and timing.
 
	
 
N/A
 

Secondary			
Efficacy	
 
To evaluate anti-myeloma activity of elranatamab in combination with lenalidomide and dexamethasone
 
	
 
ORR and CRR, per IMWG response criteria as determined by investigator;
 
Time to event endpoints: TTR, DOR, DOCR, PFS per IMWG response criteria as determined by investigator, and OS;
 
MRD (assessed by central lab) negativity rate per IMWG sequencing criteria.
 
	
 
N/A
 

PK	
 
To evaluate the PK of elranatamab given alone and in combination with lenalidomide and dexamethasone.
 
To evaluate the PK of lenalidomide when administered with elranatamab
 
	
 
PK parameters (free and total elranatamab) in serum: <math>C_{max}</math>, <math>T_{max}</math>, <math>AUC_{last}</math> after elranatamab administration alone as a priming dose;
 
Pre- and post-dose concentrations of elranatamab in combination with
 
	
 
N/A
 

090177e1993a4a6d\Approved\Approved On: 31-Jan-2022 16:54 (GMT)

		lenalidomide and dexamethasone; 
 
• Trough plasma concentrations of lenalidomide at selected cycles.
 
	
Immunogenicity	
 
• To evaluate immunogenicity of elranatamab in combination with lenalidomide
 
	
 
• Incidence and titers of ADA and NAb against elranatamab.
 
	
 
• N/A
 

Tertiary/Exploratory			
Efficacy	
 
• To explore additional efficacy of elranatamab in combination with lenalidomide and dexamethasone.
 
	
 
• sMRD negativity rate and DOMRD negativity.
 
	
 
• N/A
 

PRO	
 
• To assess the impact of elranatamab on patient-reported symptoms and functioning
 
	
 
• EORTC QLQ-CIPN20.
 
	
 
• N/A
 

Biomarker	
 
• To understand the relationship between elranatamab in combination with lenalidomide and dexamethasone and the biology of the participant’s MM
 
	
 
• Measurements of biomarkers (DNA, RNA, protein, or defined cell types) resulting from analyses of peripheral blood and/or BM biospecimens.
 
	
 
• N/A
 

	
 
• To explore correlations between elranatamab exposure and efficacy, safety and biomarker endpoints, if data allow.
 
	
 
• Selected PK, efficacy, safety and biomarker endpoints.
 
	
 
• N/A
 

## 2.2. Study Design

This sub-study of C1071004 protocol will evaluate safety, efficacy, PK, and pharmacodynamics of elranatamab in combination with lenalidomide and dexamethasone in participants with Relapsed/refractory multiple myeloma (RRMM). The sub-study is composed of 2 parts for the Phase 1b portion:

- **Dose escalation part** is to evaluate the tolerability, safety and select a recommended dose and regimen for elranatamab in combination with lenalidomide and dexamethasone (combination RP2D).

- **Dose expansion part** is to further evaluate the overall safety at combination RP2D.

### Dose Escalation Design:

[figure not shown]
Approximately 3-6 DLT-evaluable participants will be treated at each dose level of the combination therapy. If DL1 is tolerated, two cohorts (DL2a and DL2b) will be initiated in parallel and arm allocation for participants follows an alternative allocation scheme. DL2a and DL2b must be considered tolerable before DL3 can be opened. Before moving to the next dose level, the safety data will be evaluated by a dose level review committee once evaluable participants have been followed for a minimum of 42 days after the first dose of elranatamab (14 days from the first elranatamab dose + first 28 days following the first dose of the combination of elranatamab, lenalidomide, and dexamethasone).

Dose escalation/de-escalation decisions will be guided by a BLRM approach to determine the MTD of elranatamab when administered in combination with lenalidomide and dexamethasone. However, other evidence such as safety data beyond DLT window, clinical activity, PK, and pharmacodynamics data will also be evaluated in determining the RP2D. The RP2D will be determined with agreement between the investigators and the Sponsor at the dose level review committee.

### Dose Expansion Design:

The dose expansion part will begin once the combination RP2D is identified in the dose escalation part. A total of up to 20 participants (including 6 participants treated at the RP2D from the dose escalation part) will be enrolled and dosed at RP2D in the dose expansion part.

**Figure 1. Study Design**

090177e1993a4a6d\Approved\Approved On: 31-Jan-2022 16:54 (GMT)

### **3. ENDPOINTS AND BASELINE VARIABLES: DEFINITIONS AND CONVENTIONS**

#### **3.1. Primary Endpoints**

##### **3.1.1. Dose Escalation**

The primary endpoint of the dose escalation part is the DLTs during the DLT observation period, which is the first 42 days from Cycle 0 Day 1 through Cycle 1 Day 28 of study intervention.

##### **3.1.2. Dose Expansion**

The primary endpoints in the dose expansion part are as follows:

- AEs as characterized by type, frequency, severity, timing, seriousness, and relationship to elranatamab in combination with lenalidomide and dexamethasone;
- Laboratory abnormalities as characterized by type, frequency, severity and timing.

#### **3.2. Secondary Endpoints**

##### **3.2.1. Efficacy Endpoints**

For all efficacy endpoints per IMWG response criteria, BOR assessed based on reported overall responses recorded at evaluation time points from the date of first dose until the first documentation of confirmed PD, death or start of new anti-cancer therapy, whichever occurs first.

- Objective response is defined as having a BOR of confirmed sCR, CR, VGPR or PR.

###### **3.2.1.1. Objective Response Rate**

Objective response rate (ORR) is defined as the proportion of participants with an objective response per IMWG response criteria as determined by investigator.

###### **3.2.1.2. Complete Response Rate**

Complete response rate (CRR) is defined as the proportion of participants with a BOR of confirmed CR/sCR per IMWG criteria as determined by investigator.

###### **3.2.1.3. Duration of Response**

Duration of response (DOR) is defined, for participants with an objective response per IMWG criteria as determined by investigator, as the time from the first documentation of objective response that is subsequently confirmed, until the initial PD date that is subsequently confirmed per IMWG criteria, or death due to any cause, whichever occurs first.

### 3.2.1.4. Duration of Complete Response

Duration of complete response (DOCR) is defined, for participants with a BOR of confirmed CR/sCR per IMWG criteria as determined by investigator, as the time from the first documentation of CR/sCR that is subsequently confirmed, until the initial documentation of PD date that is subsequently confirmed per IMWG criteria, or death due to any cause, whichever occurs first.

### 3.2.1.5. Progression-free Survival

Progression-free survival (PFS) is defined as the time from the date of first dose until the initial documentation of PD date that is subsequently confirmed per IMWG criteria as determined by investigator, or death due to any cause, whichever occurs first.

### 3.2.1.6. Overall Survival

Overall survival (OS) is defined as the time from the date of first dose until death due to any cause.

### 3.2.1.7. Time to Response

Time to response (TTR) is defined, for participants with an objective response per IMWG criteria as determined by investigator, as the time from the date of first dose to the first documentation of objective response observed date that is subsequently confirmed. For participants with EMD at baseline, MR or better cannot be confirmed until a post-baseline EMD assessment is performed and the date of confirmed response cannot be prior to the initial EMD assessment date.

### 3.2.1.8. Minimal Residual Disease Negativity Rate

Minimal Residual Disease (MRD) (assessed by central lab) negativity rate is the proportion of participants with CR or better per investigator and negative MRD (threshold **CCI**) per IMWG sequencing criteria from the date of first dose until confirmed PD, death or start of new anticancer first therapy, whichever occurs.

### 3.2.2. Safety Endpoints

- Adverse events (AEs) and laboratory abnormalities as graded by the National Cancer Institute Common Terminology Criteria for Adverse Events (NCI CTCAE) version 5.0.
- Cytokine release syndrome (CRS) and immune cell-associated neurotoxicity syndrome (ICANS) graded according to ASTCT criteria.

### 3.2.3. Pharmacokinetic Endpoints

- Free and total PK parameters of elranatamab in serum:  $C_{max}$ ,  $T_{max}$ ,  $AUC_{last}$  after elranatamab administration alone as a priming dose;
- Pre- and post-dose concentrations (free and total) of elranatamab in combination with lenalidomide and dexamethasone;

- Trough serum concentrations of lenalidomide at selected cycles.

### 3.2.4. Immunogenicity Endpoints

- Incidence and titers of ADA and NAb against elranatamab.

## 3.3. Exploratory Endpoints

### 3.3.1. Additional Efficacy Endpoints

- Sustained MRD (sMRD) negativity rate and duration of MRD (DOMRD) negativity.

### 3.3.2. Translational Oncology Biomarkers Endpoints

- Measurements of biomarkers (DNA, RNA, protein or defined cell types) resulting from analyses of peripheral blood, and/or BM biospecimens.
- Selected PK, efficacy, safety, and biomarker endpoints

### 3.3.3. Patient-Reported Outcomes Endpoints

Patient-reported outcomes (PROs) are measured using the following instruments:

European Organization for Research and Treatment of Cancer - chemotherapy-induced peripheral neuropathy (EORTC QLQ-CIPN20): The EORTC QLQ-CIPN20 is a module developed by the EORTC group to assess chemotherapy-induced peripheral neuropathy. It contains 20 items which can be grouped into a sensory subscale (9 items), motor subscale (8 items) and autonomic subscale (3 items).

## 3.4. Baseline Variables

See [Section 3.4 of the master SAP](#) for the definition of baseline variables.

## 3.5. Safety Endpoints

See [Section 3.5 of the master SAP](#) for the definition of the safety endpoints.

## 4. ANALYSIS SETS (POPULATIONS FOR ANALYSIS)

See [Section 4 of the master SAP](#) for definitions of analysis sets.

## 5. GENERAL METHODOLOGY AND CONVENTIONS

[figure not shown]
### 5.1. Hypotheses and Decision Rules

#### 5.1.1. Hypotheses and Sample Size

##### 5.1.1.1. Phase 1b Dose Escalation

The primary objective in the Phase 1b dose escalation part of the study is to assess safety and tolerability of elranatamab in combination with lenalidomide and dexamethasone in order to select a RP2D for the combination therapy. There is no statistical hypothesis for this part. A BLRM will be utilized for dose escalation recommendation of the combination therapy.

CCI

### **Sample Size Estimation**

A minimum of 3-6 DLT-evaluable participants (as defined in [Section 4 in the master SAP](#)) will be treated at each dose level of the combination therapy. The actual number of participants to be enrolled will depend on the number of dose levels evaluated and the number of participants treated at each dose level. Therefore, it cannot be determined in advance.

090177e1993a4a6d\Approved\Approved On: 31-Jan-2022 16:54 (GMT)

It is estimated that approximately up to 24 DLT evaluable participants will be enrolled and treated with elranatamab combination in the dose escalation part which will include at least 6 DLT evaluable participants treated at the elranatamab combination RP2D level.

If any participant is deemed non-evaluable for DLT, additional participants may be enrolled to ensure there are a sufficient number of evaluable participants in the Phase 1b of the sub-study.

#### **5.1.1.2. Phase 1b Dose Expansion**

The primary objective in the Phase 1b dose expansion part of the study is to further evaluate the overall safety profile of elranatamab in combination with lenalidomide, and dexamethasone at RP2D. There is no statistical hypothesis for this part.

Dose expansion phase will begin once the combination RP2D is identified in the dose escalation part. A total of up to 20 participants will be enrolled and dosed at RP2D in the dose expansion part, including the 6 participants treated at the RP2D level from dose escalation part.

#### **5.1.2. Decision Rules**

##### **5.1.2.1. Phase 1b Does Escalation**

[figure not shown]
###### **Identification of RP2D**

Dose escalation/de-escalation decisions will be guided by a BLRM approach, through the posterior probability of DLT during the DLT observation period, to determine the MTD of elranatamab when administered in combination with lenalidomide and dexamethasone. BLRM takes available DLT data from all dose levels when updating posterior probability of DLT. Specifically, dose level 2a and 2b will be tested in parallel once dose level 1 is cleared. The DLT data on both dose level 2a and 2b will be used by the BLRM to recommend next dose level. However, other evidence such as safety data beyond DLT window, clinical activity, PK, and pharmacodynamics data will also be evaluated in determining the RP2D. The RP2D will be determined with agreement between the investigators and the Sponsor at the dose level review committee.

###### **Assessment of Participant Risk**

After each dosing cohort of participants completes the DLT observation period, the posterior distribution for the risk of DLT for each dose combination will be evaluated. The posterior distributions will be summarized to provide the posterior probability that the risk of DLT lies within the following intervals.

- Underdosing: [0, 0.16);
- Target toxicity: [0.16, 0.33);
- Excessive toxicity: [0.33, 1].

### 5.1.2.2. Phase 1b Dose Expansion

Overall safety profile of elranatamab in combination with lenalidomide and dexamethasone at RP2D will be further studied in the dose expansion part. There is no decision rule for the dose expansion part of the study. The following table lists the probability of detecting a given DLT in at least 1 participant under a possible range of true rare DLT probability. For example, the dose expansion with n=20 participants will have 64% chance to detect a rare DLT in at least 1 patient when the true DLT probability is 5%.

True DLT probability	1%	3%	5%	7%	10%
Prob of detecting DLT in $\geq 1$ patient	0.18	0.46	0.64	0.77	0.88

The final analysis will be conducted once all participants have been followed for at least 2 years from enrollment or have otherwise discontinued from the treatment.

## 5.2. General Methods

Unless otherwise specified, all analyses will be performed for dose escalation and expansion separately and with the cohort of RP2D in dose escalation and expansion combined.

For the dose escalation part of the study, all analyses will be performed by dose level and with all dose levels combined as well.

See [Section 5.2 of the master SAP](#) for the detail of the general statistical methods.

## 6. ANALYSES AND SUMMARIES

### 6.1. Primary Endpoints

#### 6.1.1. Phase 1b Dose Escalation

DLT rate is calculated as the number of DLT-evaluable participants with DLTs in the DLT observation period divided by the number of DLT-evaluable participants in the DLT observation period.

Analyses of DLT will be performed on DLT Evaluable Analysis Set as defined in [Section 4 of the master SAP](#). DLT rate will be summarized and listed by dose levels.

### 6.1.2. Phase 1b Dose Expansion

The primary endpoints in the dose expansion part are as follows:

- AEs as characterized by type, frequency, severity, timing, seriousness, and relationship to elranatamab combination with lenalidomide and dexamethasone;
- Laboratory abnormalities as characterized by type, frequency, severity and timing.

See [Section 6.6 of the master SAP](#) for safety summaries and analyses.

## 6.2. Secondary Efficacy Endpoints

### 6.2.1. Objective Response

The observed point estimate of ORR will be calculated along with the 2-sided 95% CIs using the Clopper-Pearson method (exact CI for a binomial proportion).

The frequency (number and percentage) of participants with BOR by investigator in each response category will be summarized: sCR; CR; VGPR; PR; MR; SD; PD; Not evaluable (NE).

In addition, the following response categories will be calculated along with corresponding 2-sided exact 95% CIs using the Clopper-Pearson method:

- VGPR or better (sCR + CR + VGPR);
- Clinical benefit (sCR + CR + VGPR + PR + MR).

BOR will be assessed based on reported timepoint responses by investigator recorded at evaluation time points from the date of first dose until confirmed disease progression, death or start of new anticancer therapy using IMWG response criteria. BOR needs to be confirmed according to IMWG response criteria ([Table 2](#)). If a participant meets multiple criteria in determining confirmed BOR, the order of criteria in this table will be used to define the hierarchy. Twenty-eight days is required between the disease assessments, but a different sample is required for confirmation. A confirmatory response assessment may be performed >28 days following the initial response assessment, allowing for a maximum of 1 intervening missing or not evaluable assessment.

The rules for PD confirmation apply to both confirmed PD as BOR and confirmed PD after BOR (for time-to-event endpoint analyses), and the PD date is the date of the initial documentation of PD date.

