10.11. Appendix 11: IMWG Response Criteria for Multiple Myeloma

Participants must have measurable disease at enrollment (study entry) as defined by:

- Serum M protein ≥ 0.5 g/dL (5 g/L);
- Urine M protein ≥ 200 mg/24 hours;
- Serum FLC assay: involved FLC level ≥ 10 mg/dL (≥ 100 mg/L) AND abnormal serum immunoglobulin kappa to lambda FLC ratio (< 0.26 or > 1.65).

Whenever more than 1 parameter is used to assess response, the overall assigned level of response is determined by the lowest level of response.

All response assessments will be entered on the CRF.

All response categories require 2 consecutive assessments made any time before starting new therapy. To confirm response or PD, 2 discrete samples are required, and testing cannot be based upon the splitting of a single sample.

Response ^a	Modified IMWG Criteria
Sustained MRD-negative	
 • CR as defined below plus: • MRD negativity in the marrow (NGF or NGS, or both) and by imaging as defined below, confirmed minimum of 1 year apart. Subsequent evaluations can be used to further specify the duration of negativity (eg, MRD-negative at 5 years)
Flow MRD-negative	
 • CR as defined below plus: • Absence of phenotypically aberrant clonal plasma cells by NGF on BMA using the EuroFlow standard operation procedure for MRD detection in MM (or validated equivalent method) with a minimum sensitivity of 1 in 10^5 nucleated cells or higher
Sequencing MRD-negative	
 • CR as defined below plus: • Absence of clonal plasma cells by NGS on BMA in which presence of a clone is defined as less than 2 identical sequencing reads obtained after DNA sequencing of BMA using the LymphoSIGHT platform (or validated equivalent method) with a minimum sensitivity of 1 in 10^5 nucleated cells or higher
Imaging plus MRD-negative	
 • CR as defined below plus: • MRD negativity as defined by NGF or NGS plus disappearance of every area of increased tracer uptake found at baseline or a preceding PET/CT or decrease to less mediastinal blood pool SUV or decrease to less than that of surrounding normal tissue

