Progressive Disease (PD) ^{b,e,f}	
Any 1 or more of the following criteria:
 
 Increase of ≥25% from lowest confirmed response value in any 1 or more of the following:^{e,f} Serum M-component (the absolute increase must be ≥0.5 g/dL); Serum M-protein increase ≥1 g/dL, if the lowest M component was ≥5 g/dL; Urine M-protein (the absolute increase must be ≥200 mg/24 h). In participants without measurable serum and urine M-protein levels, the difference between involved and uninvolved serum FLC levels (absolute increase must be >10 mg/dL); In patients without measurable serum and urine M-protein levels and without measurable involved serum FLC levels, bone marrow plasma-cell percentage irrespective of baseline status (absolute increase must be ≥10%). Appearance of a new lesion(s), ≥50% increase from nadir in SPD of >1 lesion, or ≥50% increase in the longest diameter of a previous lesion >1 cm in short axis.^d ≥50% increase in circulating plasma cells (minimum of 200 cells per μL) if this is the only measure of disease

a All response categories require 2 consecutive assessments made any time before starting new therapy. Each category (except stable disease) will be considered unconfirmed until confirmatory test is performed. All categories (stable disease or better) require no known evidence of PD, new bone lesions or EMD plasmacytomas if imaging studies were performed; imaging studies are not required to satisfy these response requirements except for requirement of FDG PET to confirm imaging plus MRD-negative.

Response ^a	Modified IMWG Criteria
b	Bone marrow assessments do not need to be confirmed. Careful attention should be given to new positive immunofixation results appearing in participants who have achieved a CR, when the isotype is different. This often represents oligoclonal immune reconstitution and should not be confused with relapse; these bands typically disappear over time.
c	Presence/absence of clonal cells is based upon the κ/λ ratio. An abnormal κ/λ ratio by IHC or immunofluorescence requires a minimum of 100 plasma cells for analysis. An abnormal ratio reflecting presence of an abnormal clone is κ/λ of $>4:1$ or $<1:2$.
d	Plasmacytoma measurements should be taken from the CT portion of the PET/CT, or dedicated CT scans where applicable. Measurement of tumor size will be determined by the SPD.

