e	PD confirmation requires two consecutive assessments made at any time prior to the institution of any new anticancer therapy. If alternate therapy is started before confirming PD, any additional testing during subsequent therapy can be used to confirm PD. Participants will be considered to have PD if they meet the criteria for progression by a variable that was not considered measurable at baseline; however, for participants who had a measurable serum or urine M-protein (M-spike) at baseline, PD cannot be defined by increases in serum FLC alone.
f	For PD, serum M-component increases of ≥ 1 mg/dL are sufficient to define relapse if starting M-component is ≥ 5 g/dL.

ADDITIONAL NOTES:

- If participants do not have measurable disease at baseline they can only be assessed for at least a CR or PD.
- Serum FLC levels should only be used for response assessment when both the serum and urine M-component levels are deemed not measurable (including at suspected CR).
- In cases where SPEP is found to be unreliable (eg, IgA, IgD myelomas) for M-protein assessment, quantitative immunoglobulin measurements are preferred for disease assessment; the same percentage changes apply as for serum M-protein. If used, quantitative immunoglobulin assessment must be used exclusively for a participant (ie, quantitative immunoglobulin and SPEP cannot be used interchangeably for disease assessment of the same participant).

Source: Adapted from (Kumar et al, 2016)

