**Table 2. Derivation Rules for Confirmed Best Overall Response per IMWG Response Criteria**

Scenario	Timepoint Response at:			BOR
	Assessment 1	Assessment 2	Assessment 3	
1	sCR	sCR		sCR
2	sCR	NE	sCR	
3	CR/VGPR/PR/MR/SD/PD c	sCR	sCR	
4	CR	sCR/CR		CR
5	sCR/CR	CR		
6	CR	NE	CR	
7	VGPR/PR/MR/SD/PD c	CR	CR	
8	VGPR	sCR/CR/VGPR		VGPR
9	sCR/CR/VGPR	VGPR		
10	VGPR	NE	VGPR	
11	PR/MR/SD/PD c	VGPR	VGPR	
12	PR	sCR/CR/VGPR/PR		PR
13	sCR/CR/VGPR/PR	PR		
14	PR	NE	PR	
15	MR/SD/PD c	PR	PR	
16	MR	sCR/CR/VGPR/PR/MR		MR
17	sCR/CR/VGPR/PR/MR	MR		
18	MR	NE	MR	
19	SD/PD c	MR	MR	
20	SD	No further assessments		SD a
21	SD	sCR/CR/VGPR/PR/MR /SD/PD	No further assessments	
22	sCR/CR/VGPR/PR/MR	NE/PD or no further assessment	No further assessments	
23	PD c	PD (any reason) including PD after initiation of new anticancer therapy		PD
24	PD c	Participant died due to disease before further disease assessment (including death due to disease under study after initiation of new anticancer therapy)		

090177e1993a4a6d\Approved\Approved On: 31-Jan-2022 16:54 (GMT)

Scenario	Timepoint Response at:			BOR
	Assessment 1	Assessment 2	Assessment 3	
25	PD (due to EMD, or bone marrow plasma cells) b	sCR/CR/VGPR/PR/MR /SD/NE/PD or no further assessments	No further assessments	
26	Death (due to disease under study)			
27	Death (not due to disease under study) before initiation of new anticancer therapy			
28	NE	No further assessment		
29	NE	NE/PD c	No further assessments	NE
30	PD c	sCR/CR/VGPR/PR/MR /SD/NE	No further assessments	
EMD = extramedullary disease; IMWG = International Myeloma Working Group, sCR = stringent complete response, CR = complete response, PR = partial response, VGPR = very good partial response, SD = stable disease, PD = progressive disease, NE = not evaluable. a. SD does not need to be confirmed. b. PD due to EMD (includes any new lesion, increased extramedullary or paramedullary lesions, plasmacytomas), or bone marrow plasma cells does not need to be confirmed. c. PD due to reasons other than EMD, or bone marrow plasma cells.				

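### Sub-study B SAP 6.2.1 words 28 days between disease assessments as a requirement, which the master SAP and the current protocol do not; a minor wording fix

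*SAP*

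**What the plan says.** Section 6.2.1 of the Sub-study B SAP derives best overall response (BOR) from the investigator's timepoint responses and says that confirmation follows the IMWG criteria as laid out in its Table 2. It then adds: "Twenty-eight days is required between the disease assessments, but a different sample is required for confirmation". The next sentence deals with the late side of the window: "A confirmatory response assessment may be performed >28 days following the initial response assessment", with at most one missing or not evaluable assessment in between.

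On the same question the current protocol says, in Appendix 11: "All response categories require 2 consecutive assessments made any time before starting new therapy", and "To confirm response or PD, 2 discrete samples are required". For progression, footnote e says: "PD confirmation requires two consecutive assessments made at any time prior to the institution of any new anticancer therapy". Footnote b exempts marrow: "Bone marrow assessments do not need to be confirmed". Protocol section 8.1 also asks for two consecutive assessments and gives no interval.

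The master SAP (6.1.2, Phase 2) states that there is no minimum interval and that the confirming sample must be a different one. The Sub-study A SAP (6.1.2, Phase 2) describes 28 days as the planned spacing after cycle 1 and provides for confirmation on the same day if another sample is used.

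**The concern.** Only the Sub-study B sentence turns 28 days into a requirement. Taken at its word, it would reject a pair of assessments that the master SAP and the current protocol accept, inside a paragraph that says confirmation follows the IMWG criteria. A minimum set equal to the planned four-week spacing, with no tolerance, is also awkward. The master SAP's PFS table works with a 3-day visit window, and protocol 7.1.2 allows plus or minus one week for assessments after treatment stops. If similar windows apply on treatment in Sub-study B (an assumption), a visit could be on schedule and still fail to confirm.

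At stake are the endpoints that count confirmed responders: ORR, CRR, and MRD negativity with confirmed sCR/CR. Two programmers could read the section differently and report different rates, and response in Sub-study B could be defined differently from response in Sub-study A.

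**Working it through.** No figure in the plan depends on the confirmation interval, so there is none to reproduce. The check compares the sources, follows the literal rule through Table 2, and then sizes the effect.

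**1. The sources side by side**

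| Source | Minimum gap | Different sample |
|---|---|---|
| Master SAP 6.1.2 (March 2021) | none, stated | yes |
| Sub-study B SAP 6.2.1 (January 2022) | 28 days, worded as required | yes |
| Sub-study B SAP Table 2 | not addressed | not addressed |
| Protocol Appendix 11 (current, Amendment 8) | none; any time before new therapy | yes |
| Sub-study A SAP 6.1.2 (June 2024) | none stated; 28 days is the schedule | yes, if on the same day |

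**2. The sentence itself.** Its second half begins with a contrast and then asks for a different sample. That contrast makes sense after a statement that no minimum applies. It does not after a 28-day requirement, because samples 28 days apart are different anyway. The sentence after it reads naturally as an extension of a 28-day schedule. Both features point to an edit of the master SAP wording that was left half done.

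**3. The literal rule in Table 2** (constructed examples)
- PR, then PR 27 days later, then no further assessment. Under the master SAP rule this is scenario 12, BOR of PR. Under the literal 28-day rule the second PR does not confirm the first. Table 2 has no row for two responses that are too close together. A programmer who ignores the sentence stays in scenario 12. One who drops the second assessment reaches scenario 22, where the second entry is "NE/PD or no further assessment" and BOR is SD.
- PR, then CR at least 28 days later, then CR 27 days after that. The CR pair is too close, but PR followed by CR still meets scenario 12, so BOR is PR. ORR is unchanged and CRR loses one. With an earlier VGPR, scenario 8 gives VGPR.
- Any responder with a later qualifying assessment is confirmed then.

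**4. Size of one lost response.** The combined RP2D cohort is up to 20 participants, 6 of them from escalation (Sub-study B SAP 2.2), and results are also shown separately for escalation and expansion (5.2).
- Combined: 100/20 = 5.0 points.
- Expansion alone: 100/(20 − 6) = 100/14 = 7.1 points.
- Example with 95% Clopper-Pearson intervals: 12/20 = 60% (36.1 to 80.9) becomes 11/20 = 55% (31.5 to 76.9).

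**5. Order of magnitude, by assumption.** The documents do not say how many responders would have only two responding visits. As a rough guide, take the monotherapy figures in protocol 2.2.3.2: ORR 61.0%, and 84.4% of responders still in response at 9 months (95% CI 72.7 to 91.4). Assume a constant hazard and visits nominally 28 days apart.
- Hazard per day: h = −ln(S9)/(9 × 30.4375).
- Probability of exactly two responding visits: P = exp(−28h) − exp(−56h).
- S9 = 0.844 gives P = 0.0169; S9 = 0.727 gives 0.0310; S9 = 0.914 gives 0.0091.
- Expected responders: 0.61 × 20 = 12.2.
- If every such pair were under 28 days apart, the expected loss is 12.2 × P = 0.21 responders (0.11 to 0.38), or 1.03 ORR points (0.55 to 1.89) at n = 20. If none were, the loss is 0.

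These are confirmed responders on another regimen, and early discontinuation or new therapy would add some cases. The calculation indicates scale only.

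**The case against.** The strongest reply has four parts.

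*Versions.* The Sub-study B SAP is based on Amendment 6 (December 2021). The Appendix 11 text we can read is Amendment 8, and the amendment history says Amendment 7 revised that appendix. The Sub-study A SAP came more than two years later. A reader might infer that this SAP broke the protocol it was written to. The documents do not support that, because the Amendment 6 wording is not available. What stands is the conflict with the master SAP, which predates this SAP and which it names as the source of general methods, and with the protocol as it now reads.

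*Intent.* Section 2 of the Sub-study B SAP lets it set its own methods, and the Sub-study B protocol is not available. A deliberate rule therefore cannot be excluded. But the section gives no reason for one and itself invokes the IMWG criteria.

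*Table 2.* It is tempting to count Table 2 as a further contradiction, or to say that a close pair becomes SD. Neither follows. The table orders assessments and says nothing about spacing, and PR followed by PR literally matches scenario 12. SD is an inference about how someone might code it.

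*Reading and size.* The 28 days can be read as describing the schedule, which does no harm. A reader might also infer that several responses would be lost. The illustration above does not support that: its largest expected loss is about 0.2 of a responder, or 0.38 at the extreme of the interval.

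These points narrow the consequence and the certainty about intent. They do not remove the mismatch in a stated derivation rule.

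**Conclusion.** The point holds as a minor one. The sentence conflicts with the master SAP, the current Appendix 11 and the Sub-study A SAP, and is probably an editing slip. It does harm only if coded literally, and then only where two qualifying assessments fall less than 28 days apart with no later qualifying assessment. Most likely zero or one participant is affected. The true number cannot be derived from the documents.

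ORR, CRR and MRD negativity with confirmed sCR/CR are secondary and descriptive in Sub-study B. The primary endpoints are DLTs and safety, expansion has no hypothesis and no decision rule, and none of that changes.

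A reader might also infer a bias in PFS or DOR, because the sentence speaks of disease assessments in general. Its reach to PD is unclear. The PFS, DOR and DOCR sections send PD confirmation to Table 2, and an unconfirmed PD would also lengthen the window in which BOR is assessed. No net direction can be claimed.

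**What to change.** In Sub-study B SAP 6.2.1, replace the sentence with the one the master SAP uses in 6.1.2: no minimum interval, different sample. If 28 days is worth mentioning, call it the scheduled gap, as the Sub-study A SAP does. Keep the next sentence on later confirmation. Add that PD confirmation follows the same rule, except for PD due to EMD or marrow plasma cells, which under Table 2 footnote b ("or bone marrow plasma cells does not need to be confirmed") stands without confirmation.

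If a 28-day minimum is really intended for Sub-study B, give the reason, reconcile it with Appendix 11 and the master SAP, and add a row to Table 2 for two responses closer than 28 days.

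The first option costs one replaced sentence and one added, with no change to any primary endpoint or sample size. It should be settled before BOR is programmed.
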